## 10.4 Early Withdrawal Visit

1. Perform clinician-administered assessments (C-SSRS-R, HAM-A, HAM-D)
2. Complete self-report surveys (PCL-5, GAD-Q-IV, PHQ-9, PSQI, SF-12)
3. Record adverse events, if applicable
4. Complete blinding assessment, usability survey, and Study Completion Questionnaire
5. Return of all device and study materials
6. Participant reimbursement

## 11 ADVERSE EXPERIENCE REPORTING, DOCUMENTATION, AND MONITORING

### 11.1 Definitions

#### 11.1.1 Adverse Event (AE)

An adverse event (AE) is any untoward medical occurrence in a subject during participation in the clinical study or with use of the experimental agent being studied. An adverse finding can include a sign, symptom, abnormal assessment (laboratory test value, vital signs, electrocardiogram finding, etc.), or any combination of these regardless of relationship to participation in the study.

#### 11.1.2 Unanticipated Problem (UP)

The Office for Human Research Protections (OHRP) considers unanticipated problems (UPs) involving risks to subjects or others to include, in general, any incident, experience, or outcome that meets **all** of the following criteria:

- Unexpected in terms of nature, severity, or frequency given (a) the research procedures that are described in the protocol-related documents, such as the IRB-approved research protocol and informed consent document; and (b) the characteristics of the subject population being studied;
- Related or possibly related to participation in the research (“possibly related” means there is a reasonable possibility that the incident, experience, or outcome may have been caused by the procedures involved in the research); and
- Suggests that the research places subjects or others at a greater risk of harm (including physical, psychological, economic, or social harm) than was previously known or recognized.

#### 11.1.3 Serious Adverse Event (SAE)

A serious adverse event (SAE) is defined as any AE that meets one or more of the following criteria:

- Results in death
- Is life-threatening (places the study participant at immediate risk of death from the event as it occurred)

- Results in inpatient hospitalization or prolongation of existing hospitalization
- Results in a persistent or significant disability or incapacity
- Results in a congenital anomaly or birth defect.

An important medical event that may not result in death, be life threatening, or require hospitalization may be considered an SAE when, based upon appropriate medical judgment, the event may jeopardize the subject and may require medical or surgical intervention to prevent one of the outcomes listed in this definition.

## **11.2 Time Period and Frequency for Event Assessment and Follow-Up**

Unanticipated problems will be recorded in the data collection system throughout the study.

The PI will record all reportable events with start dates occurring any time after informed consent is obtained until 7 (for non-serious AEs) or 30 days (for SAEs) after the last day of study participation. At each study visit, the investigator or clinical research coordinator will inquire about the occurrence of AE/SAEs since the last visit. Events will be followed for outcome information until resolution or stabilization.

## **11.3 Characteristics of an Adverse Event**

### **11.3.1 Relationship to Study Intervention**

To assess relationship of an event to study intervention, the following guidelines are used:

1. Related (Possible, Probable, Definite)
  - a. The event is known to occur with the study intervention.
  - b. There is a temporal relationship between the intervention and event onset.
  - c. The event abates when the intervention is discontinued.
  - d. The event reappears upon a re-challenge with the intervention.
2. Not Related (Unlikely, Not Related)
  - a. There is no temporal relationship between the intervention and event onset.
  - b. An alternate etiology has been established.

### **11.3.2 Expectedness of SAEs**

The Study PI and Independent Safety Monitors will be responsible for determining whether an SAE is expected or unexpected. An AE will be considered unexpected if the nature, severity, or frequency of the event is not consistent with the risk information previously described for the intervention.

### **11.3.3 Severity of Event**

The following scale will be used to grade adverse events:

1. Mild: no intervention required; no impact on activities of daily living (ADL)
2. Moderate: minimal, local, or non-invasive intervention indicated; moderate impact on ADL
3. Severe: significant symptoms requiring invasive intervention; subject seeks medical attention, needs major assistance with ADL.

#### 11.4 Reporting Procedures

AEs will be monitored at frequent intervals during the study. Study participants will be monitored during the study at each clinic visit for expected and unexpected AEs related to the Empower Neuromodulation System. The Site PI or research coordinator will probe, via discussion with the participant, for the occurrence of AEs during each participant visit and record the information in the AE case report form (CRF). AEs will be described by duration (start and stop dates), severity, outcome, treatment and relation to study device, or if unrelated, the cause.

During the study, site clinical research personnel will note any change in the participant's symptoms (anxiety, depression, etc.) and the occurrence and nature of any AEs. Important clinical information that comes to light during study participation will be communicated by research coordinators to the study PI in real time.

The study investigator (either the Site PI, [name], or, in her absence, the Site co-investigator, [name]) will review each participant's safety at each study visit.

- Moderate and severe AEs reported by participants will be reviewed on the same day as they are reported by the study participant. Mild AEs reported by participants will be reviewed within 72 hours of being reported by the study participant.
- Adverse effect assessment will be done by the research coordinators and discussed with the Site PI on a daily basis, immediately after these AEs are reported by the participant to the study coordinator.

The Site PI, if not immediately present at the time of adverse effect data collection, will be contacted in real time by the study coordinator by phone, pager, or text message, so that AEs can be discussed with the Site PI.

At least every 6 months, the Site PI will report to the independent monitoring committee and study sponsor the assessment of the potential relatedness of each AE to protocol procedure, studied disease state, and study device via the CRF. For each AE recorded on the AE CRF, the PI will make an assessment of seriousness, severity, and causality.

The PI will follow all unresolved AEs until the event has resolved to baseline grade or better, the event is assessed as stable by the PI, new therapy is initiated, the participant is lost to follow-up, the participant withdraws consent, or until 7 (for non-serious AEs) or 30 days (for SAEs) after the last day of study participation.

Every effort will be made to follow all SAEs considered to be related to study procedures until a final outcome can be reported. During the study period, resolution of AEs (with dates) will be documented on the AE CRF and in the participant's medical record to facilitate source data verification. If, after follow-up, return to baseline status or stabilization cannot be established, an explanation should be recorded on the AE CRF.

In the event that an SAE or death occurs, the event will be reported by the Site PI within 48 hours after she first learns of the event to the sponsor and the reviewing IRB per the UNMC IRB reporting requirements. The initial report of an SAE must be made by phone as well as by email. The sponsor will immediately conduct an evaluation of the SAE(s) and report the results of the evaluation to FDA and NCCIH within 5 working days after first receives notice of the SAE(s).

The Site PI must report any UPs within the same timeframe. The Site PI must report any protocol deviations or violations to the sponsor within 7 days of PI awareness. The Site PI must also submit all reports to the UNMC IRB in accordance with the institutional policies.

#### **11.4.1 Unanticipated Problem Reporting**

Incidents or events that meet the OHRP criteria for unanticipated problems require the creation and completion of the UP report form. To satisfy the requirement for prompt reporting, UPs will be reported using the following timeline:

- Unanticipated problems that are serious adverse events will be reported to the IRB, Independent Safety Monitors, and sponsor (who will then report to the funding agency, NCCIH) within 7 days of the investigator becoming aware of the event.
- Any other unanticipated problem will be reported to the IRB, Independent Safety Monitors, and sponsor (who will then report to the funding agency, NCCIH) within 14 days of the investigator becoming aware of the problem.

#### **11.4.2 AE Reporting**

SAEs that are unanticipated, serious, and possibly related to the study intervention will be reported to the Independent Safety Monitors, IRB, and sponsor (who will then report to the funding agency, NCCIH).

- Unexpected fatal or life-threatening AEs related to the intervention will be reported to the Independent Safety Monitors, IRB, and sponsor (who will then report to the funding agency, NCCIH) within 48 hours of the investigator becoming aware of the event. Other serious and unexpected AEs related to the intervention will be reported within 7 days.
- Anticipated or unrelated SAEs will be handled in a less urgent manner but will be reported to the Independent Safety Monitor, IRB, and sponsor (who will then report to the funding agency, NCCIH) within 7 days.
- All other AEs documented during the course of the trial will be reported to NCCIH on an annual basis by way of inclusion in the annual report and in the annual AE

summary which will be provided to NCCIH and to the Independent Monitors. The Independent Safety Monitors Report will state that all AEs have been reviewed.

#### **11.4.3 Reporting of Pregnancy**

Due to the unknown effects of transcutaneous electrical nerve stimulation (TENS) on a fetus or breastfeeding infant whose mother is receiving TENS treatment, an exclusion criterion for this study is: "Currently pregnant or breastfeeding, has been pregnant within the past 6 months or intends to become pregnant during the study period." If a study participant becomes pregnant during study participation, she will be instructed to discontinue treatment, return the study materials, and will continue to be followed up for safety monitoring. This will be reported by the Site PI to the IRB, and sponsor (who will then report to the funding agency, NCCIH) within 5 days.

#### **11.5 Halting Rules**

The study will be stopped if, in the judgment of the Site PI, there are sufficient safety concerns that arise during the conduct of the study that would indicate that participants are being harmed by the study interventions, e.g., multiple SAEs that are judged to be related to study interventions. Subsequent review of serious, unexpected, and related AEs by the Independent Safety Monitors, IRB, sponsor, or FDA or relevant local regulatory authorities may also result in suspension of further study interventions/administration of study product. The FDA and study sponsor retain the authority to suspend additional enrollment and study interventions/administration of study product for the entire study, as applicable.

### **12 DISCONTINUATION AND REPLACEMENT OF PARTICIPANTS**

#### **12.1 Early Discontinuation of Study**

A participant may be discontinued from study at any time if the participant, the investigator, or the Sponsor feels that it is not in the participant's best interest to continue. The following is a list of possible reasons for study discontinuation:

- Participant withdrawal of consent (or assent)
- The PI believes it is in the best interest of the participant to withdraw from the study. This could be due to worsening anxiety or depression symptoms, suicidal or homicidal ideation, or for other reasons that the PI determines warrant it being in the participant's best interest to discontinue study participation
- Participant is not compliant with study procedures, including not administering at least one treatment session per two week period
- AE that in the opinion of the investigator would be in the best interest of the participant to discontinue study participation
- Protocol violation requiring discontinuation of study participation
- Lost to follow-up
- Sponsor request for early termination of study
- Positive pregnancy test (females)

If a participant is withdrawn from the study due to an AE, the participant will be followed and treated by the PI until the abnormal parameter or symptom has resolved or stabilized. All participants who discontinue study participation should come in for an early discontinuation visit as soon as possible and then should be encouraged to complete all remaining scheduled visits and procedures. All participants are free to withdraw from participation at any time, for any reason, specified or unspecified, and without prejudice. Reasonable attempts will be made by the investigator to provide a reason for participant withdrawals. The reason for the participant's withdrawal from the study will be specified in the participant's source documents. Refer to Section 10 for early withdrawal procedures.

### **12.3 Withdrawal of Participants from the Study**

If a participant who does not meet enrollment criteria is enrolled, the study sponsor will be contacted. In such cases, the PI will provide information on the participant's anticipated benefit or current benefit from being enrolled in the study or continuing to receive study interventions. In addition, the PI will discontinue participants from the study in the following circumstances:

- The PI decides that the participant should be withdrawn from the study due to an SAE judged to be due to study interventions.
- The participant or his or her medical provider requests withdrawal of the participant from the study.
- The PI stops the participant's participation in the study for medical, safety, regulatory, or other reasons consistent with applicable laws, regulations, and good clinical practice (GCP).
- Per C-SSRS-R assessment at a clinic visit, the participant exhibits acute suicidality, as confirmed on the C-SSRS-R with a "Yes" response to question 4 or question 5, or to question 6 in the past 3 months
- The participant is not compliant with study procedures, including not administering at least one treatment session per two week period. Exceptions may be made after discussions with the PI, with sponsor's approval.
- The participant has not been in contact with the research staff for at least two weeks after at least three research staff attempts for contact. Exceptions may be made after discussions with the PI, with sponsor's approval.
- In the clinical judgment of the investigator, the participant's clinical condition worsens substantially and it is felt to be in the participant's best interest to obtain alternative treatment including, but not limited to, additionally psychotherapy, pharmacotherapy, hospitalization, etc.
- The participant's skin becomes too irritated to comfortably carry out the treatment sessions, and after refraining from administering a treatment session until the skin is no longer irritated, the irritation returns upon administering another treatment session.

When a participant withdraws before completing the study, the reason for withdrawal will be documented in the CRF and in the source document.

Participants who discontinue study participation early (i.e., they withdraw prior to Visit 3) should have an early discontinuation visit. Refer to Section 10 for early withdrawal procedures. Participants who withdraw after Visit 1 but prior to Visit 3 should be encouraged to come in for a final visit (and the procedures to be followed would include those listed in Section 10).

## 12.4 Replacement of Participants

Participants who withdraw from the study will not be replaced.

## 13 PROTOCOL VIOLATIONS

A protocol violation occurs when the participant, investigator, or Sponsor fails to adhere to significant protocol requirements affecting the inclusion, exclusion, participant safety and primary endpoint criteria. Protocol violations for this study include, but are not limited to, the following:

- Failure to meet inclusion/exclusion criteria
- Use of a prohibited concomitant medication
- Failure to comply with Good Clinical Practice (GCP) guidelines will also result in a protocol violation. The Sponsor will determine if a protocol violation will result in withdrawal of a participant.

When a protocol violation occurs, it will be discussed with the investigator and a Protocol Violation Form detailing the violation will be generated. This form will be signed by a Sponsor representative and the Investigator. A copy of the form will be filed in the site's regulatory binder and in the Sponsor's files.

## 14 DATA SAFETY MONITORING

### 14.1 Independent Monitoring Committee

The Independent Monitoring Committee (IMC) for this study will be comprised of up to three Independent Safety Monitors. The monitors will not be associated with this research project and will be required to work independently of the Site PI [name], or sponsor representative (and NCCIH grant PI), [name]. No member of the Committee will be allowed to have collaborated or co-published with the grant PI or Site PI within the past three years. They will be qualified to review the patient safety data generated by this study because of their unique expertise.

### 14.2 Safety Review Plan

Study progress and safety will be reviewed monthly (and more frequently if needed) by the PO. Progress reports, including patient recruitment, retention/attrition, and AEs will be provided to the Independent Safety Monitors semi-annually. An Annual Report will be compiled and will include a list and summary of AEs. In addition, the Annual Report will address (1) whether AE rates are consistent with pre-study assumptions; (2) reason for

dropouts from the study; (3) whether all participants met entry criteria; (4) whether continuation of the study is justified on the basis that additional data are needed to accomplish the stated aims of the study; and (5) conditions whereby the study might be terminated prematurely. The Annual Report will be sent to the Independent Safety Monitors and will be forwarded to the sponsor (who will submit to the funding agency, NCCIH).

### **14.3 Study Report Outline for the Independent Safety Monitors (Interim or Annual Reports)**

The study team will generate Study Reports for the Independent Safety Monitors and will provide information on the following study parameters: enrollment status, subject status, demographics, adverse events, serious adverse events, deaths, unanticipated problems, any laboratory findings for tests conducted based on adverse events. Study Report tables will be generated only from aggregate (not by group assignment) baseline and aggregate safety data for the study population.

### **14.4 Submission of On-Site Monitoring/Audit and Inspection Reports**

The IMC and sponsor (who will then submit to the funding agency, NCCIH) will receive copies of all study monitoring/audit or inspection reports within 14 day of PI receipt. Any FDA inspection report will be submitted to the IRB, IMC, and the sponsor (who will then submit to the funding agency, NCCIH).

### **14.5 Stopping Rules**

This study will be stopped prior to its completion if: (1) the intervention is associated with adverse effects that call into question the safety of the intervention; (2) difficulty in study recruitment or retention will significantly impact the ability to evaluate the study endpoints; (3) any new information becomes available during the trial that necessitates stopping the trial; or (4) other situations occur that might warrant stopping the trial.

## **15 STATISTICAL METHODS AND CONSIDERATIONS**

### **15.1 Data Sets Analyzed**

All eligible patients who receive at least one stimulation session with the study device (the Safety Population) will be included in the safety analysis.

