## PROTOCOL SYNOPSIS

TITLE	Pilot evaluation of the Empower Neuromodulation System in GAD Patients
SPONSOR	TheraNova, LLC
FUNDING ORGANIZATION	NIH-NCCIH
NUMBER OF SITES	One (1)
STUDY DESIGN	This is a double-blinded (study participant and clinician assessor), sham-controlled pilot study.
INVESTIGATIONAL DEVICE	Empower Neuromodulation System
INDICATIONS FOR USE/PATIENT POPULATION	
The Empower Neuromodulation System is intended to provide transcutaneous electrical nerve stimulation to reduce anxiety.
 
The indicated population is adults who are diagnosed with generalized anxiety disorder (GAD).

PRIMARY OBJECTIVES	The primary study objectives of this pilot study are to evaluate the feasibility and acceptability of the Empower Neuromodulation System as a daily therapy for GAD. Feasibility will be evaluated via treatment adherence (% treatment sessions completed out of the total possible) and acceptability will be evaluated via usability as assessed by the System Usability Scale (SUS) questionnaire.
SECONDARY OBJECTIVES	The secondary study objectives are to evaluate additional endpoints for feasibility (effective nerve stimulation) and acceptability (overall satisfaction with treatment) as well as endpoints for safety (device-related adverse events), effectiveness (anxiety, medication use, depression, PTSD, sleep quality, quality of life) and blinding to treatment group (blinding assessment).
NUMBER OF PARTICIPANTS	Up to 60 (our enrollment target for the intent-to-treat population is 30 participants total, so n=60 includes up to 50% screen fails).
PARTICIPANT SELECTION CRITERIA	
Inclusion Criteria:
 
 
1. <math>\geq 19</math> years old
 
2. Current diagnosis of GAD per DSM-5 via M.I.N.I. assessment by clinician
 
3. HAM-A <math>\geq 18</math>
 
4. Negative urine pregnancy test at screening (females only)
 
5. Able to provide informed consent
 
6. Capable and willing to follow all study-related procedures
 

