#### 15.4 Analysis of Secondary Endpoints

Secondary endpoints will be analyzed via the methods described below. Unless otherwise noted, for daily and weekly metrics, we will use a random-intercept linear mixed model with restricted maximum likelihood to compare results between the active and sham treatment groups. As a secondary analysis for each of these endpoints, we will evaluate the correlations for duration since last benzodiazepine dose and dose amount vs. the endpoint. If this relationship is significant for an endpoint, we will include time since last dose in our statistical analysis.

Feasibility: Effective nerve stimulation: We will calculate effective nerve stimulation (treatment sessions that elicit skin tingling as a percentage of total treatment sessions) for each participant. We will also compare effective nerve stimulation between the active and sham treatment groups (t-test).

Acceptability: Overall satisfaction with treatment: We will compare overall satisfaction with treatment scores between the active and sham treatment groups (t-test).

Safety: We will tabulate AEs across all participants. This will include tabulating the number of participants for whom the event occurred, the rate of occurrence, and the severity and relationship to the study device.

Effectiveness: Change in HAM-A score: We will compare the change in HAM-A score between the active and sham treatment groups (t-test).

Effectiveness: Change in GAD-Q-IV score: We will compare the change in GAD-Q-IV score between the active and sham treatment groups (t-test).

Effectiveness: Change in BAI score: We will compare the change in BAI score between the active and sham treatment groups (mixed models).

Effectiveness: Change in daily anxiety severity self-report: We will compare the change in daily anxiety severity scores between the active and sham treatment groups (mixed models).

Effectiveness: Change in daily anxiety interference self-report: We will compare the change in daily anxiety interference scores between the active and sham treatment groups (mixed models).

Effectiveness: Change in anxiety severity self-report as an immediate result of treatment: We will compare the short-term effect of Empower treatment on anxiety severity score (% change for post-treatment score vs. pre-treatment score) (repeated measures ANOVA with Tukey correction, active vs. sham treatment group).

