## 15.5 Randomization and Sample Size

At enrollment, participants will be randomized (1:1, [REDACTED] stratified by sex) to the active or sham stimulation. Participants will also be randomized for the body side that they should apply stimulation to first (right vs. left, 1:1 simple randomization). Men and women will be randomized separately.

As a pilot study, our primary goal is to demonstrate feasibility for GAD treatment. Accordingly, the study sample size is based on similar pilot GAD studies in the literature. For two rTMS studies, each treatment arm had 12-25 participants, with an average of 15 participants. To be consistent with these studies, we will enroll 15 participants per treatment arm, for a total of 30 participants.

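### Section 15.1 limits the Safety Population to 'eligible' treated patients; read literally, this leaves out treated participants later found ineligible and conflicts with the adverse event tabulation in Section 15.4

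*Combined protocol and SAP*

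**What the plan says.** Section 15.1 is one sentence, with no redaction marked in it: "All eligible patients who receive at least one stimulation session with the study device (the Safety Population) will be included in the safety analysis". No other analysis set is defined anywhere in the combined protocol and SAP.

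Section 12.3 provides for entry errors: "If a participant who does not meet enrollment criteria is enrolled, the study sponsor will be contacted". The PI is then to describe the participant's anticipated benefit, or "current benefit from being enrolled in the study or continuing to receive study interventions". Section 13 lists "Failure to meet inclusion/exclusion criteria" as a protocol violation and leaves it to the sponsor whether a violation leads to withdrawal.

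On the safety analysis itself, Section 15.4 says: "We will tabulate AEs across all participants". It sets no eligibility condition.

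The synopsis gives the recruitment ceiling of 60 on the basis that "our enrollment target for the intent-to-treat population is 30 participants total, so n=60 includes up to 50% screen fails", and Section 15.5 says "we will enroll 15 participants per treatment arm, for a total of 30 participants". The intent-to-treat population is mentioned only there in the synopsis and is not defined. Sections 15.3 and 15.4 name a test or model for each comparison but no analysis set for adherence, SUS or any effectiveness endpoint.

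**The concern.** A safety set normally follows exposure: whoever was stimulated is counted. Section 15.1 adds a second condition, eligibility, and the protocol itself expects that some treated people may not meet it. If an entry error comes to light after the first session, the literal wording removes that person's events from the numerator and the person from the denominator.

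Several exclusion criteria in Section 6.3 (nerve damage in the arm or hand, active implants, compromised skin at the electrode site) bear on device safety, so events in people who were entered in error are worth reporting. Section 9.1.6 screens for nerve damage and implanted devices by asking the participant, with chart review only where a chart is available, so a missed exclusion is possible.

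Because Section 15.4 points the other way, whoever writes the safety tables must choose between two denominators, and that choice could be made after the events are known.

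**Working it through.** **1. The plan's own figure.** The synopsis allows 60 participants with up to 50% screen failures: 60 × (1 − 0.5) = 30. Section 15.5 gives 2 × 15 = 30. The target of 30 reproduces. It rests on precedent from other pilot studies, so there is no power calculation to check.

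**2. Count of analysis sets.** Defined: one (Safety Population, Section 15.1). Named but undefined: one (intent-to-treat, synopsis). Assigned to a primary or effectiveness analysis: none.

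**3. Can a treated participant be ineligible?** Section 10.1 places the final eligibility review before randomisation and the first session, all at Visit 1. Section 16.8 then has the criteria of enrolled participants checked monthly to quarterly, so an error found by that route surfaces after the first session. Section 12.3 does not make withdrawal automatic. Treated but ineligible participants are therefore a foreseen group.

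**4. The two denominators.** Let k be the number of treated participants later found ineligible, with all 30 treated. Section 15.1 read literally gives 30 − k. Section 15.4 gives at least 30. Its phrase is not defined either: Section 11.2 records events from consent, so it could be read to include people screened but never treated.

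**5. Size, by assumption.** The documents give neither k nor an event rate. Assume k from 0 to 3 and 3 true device-related cases among 30.

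- If every removed participant is a case, the reported rate is (3 − k)/(30 − k):
  - k = 0: 3/30 = 10.0%
  - k = 1: 2/29 = 6.9%
  - k = 2: 1/28 = 3.6%
  - k = 3: 0/27 = 0%
- If one removed participant is not a case, the rate is 3/29 = 10.3%, slightly higher.
- If no events occur at all, the one-sided 95% upper bound is 1 − 0.05^(1/n):
  - n = 30: 9.50%
  - n = 29: 9.81%
  - n = 28: 10.15%
  - n = 27: 10.50%

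Losing denominator alone changes little, about 0.3 of a percentage point per person. The result moves materially only when the person removed had an event.

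**The case against.** The strongest answer is that 'eligible' describes status before randomisation. Sections 4.4 and 6.1 use it of people who may be randomised, and Section 10.1 finishes the eligibility review before treatment starts. On that usage the set is simply those cleared at Visit 1 and then stimulated, and nobody leaves it later. Sections 12.3 and 13 prescribe sponsor contact, a violation form and possible withdrawal; neither removes data from analysis. This stands as a plausible reading, so a flat statement that the plan drops such participants would go too far. But Section 15.1 does not define the word, and on this reading it adds almost nothing, since only cleared participants should be treated.

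Second, Sections 5.3, 9.1.11 and 11.2 collect and evaluate adverse events without an eligibility filter, and Section 15.4 tabulates them over everyone. That shows the data will exist. It does not settle which section governs the denominator.

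Third, a reader might infer that the eligible-and-treated set would also be used for adherence, SUS and effectiveness, and so damage the randomised comparison. The documents do not support this. Section 15.1 confines its set to safety, Section 15.3 calculates adherence for each participant, Section 15.4 compares the treatment groups, and the synopsis names an intent-to-treat population. What remains is missing detail. Assigning all randomised participants does not by itself settle how missing final scores are handled.

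Fourth, a larger per-arm effect could be illustrated with invented counts, or one could assume that ineligible participants are the likeliest to have events. Neither has a basis here: Section 15.4 plans tabulation across participants, not by arm, and Sections 1.3 and 17.1 report no device-related events in four other studies of the device. The first session is supervised at Visit 1 soon after randomisation, so the treated and randomised groups should nearly coincide.

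**Conclusion.** The point holds as an ambiguity and an internal conflict. Taken literally, Section 15.1 excludes exposed people whom Section 12.3 foresees, and it disagrees with Section 15.4 on the adverse event denominator. It does not establish that events will be dropped.

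The effect is zero if no treated participant is found ineligible. Under the assumed 3 cases in 30, removing one case lowers the reported rate from 10.0% to 6.9%, a difference of 3.1 percentage points; removing one non-case raises it to 10.3%. These counts are assumptions.

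The undefined and unassigned intent-to-treat population is a separate, lesser matter of completeness. It is not evidence of a biased primary or effectiveness analysis.

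**What to change.** In Section 15.1, delete 'eligible' and state: *The Safety Population is all participants given one or more stimulation sessions, whatever is later found about their eligibility.* Have the safety paragraph of Section 15.4 refer to that set, so that one denominator applies.

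As a secondary clarification, add to Section 15.1: *The intent-to-treat population is all randomised participants, analysed as randomised. Adherence, SUS and effectiveness are analysed in this population, using available data where Visit 3 or early withdrawal scores are missing.* The same edit should say how the total possible sessions are counted for a participant who withdraws, because the visible text of Section 15.3 does not.

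The safety correction costs one deleted word and a cross-reference. The clarification costs a few sentences and one decision on the adherence denominator. No new data are needed and the target stays at 30.
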